3.4 Study Population

3.4.1 Inclusion Criteria

- 1) Males or females age 8 to 16 years old at time of enrollment (inclusive)
- 2) Diagnosis of Idiopathic Scoliosis
- 3) Sanders bone age of less than or equal to 4
- 4) Thoracic curve of greater than or equal to 35 degrees, but no bigger than 60 degrees
- 5) Lumbar curve less than 35 degrees
- 6) Spina bifida occulta is permitted
- 7) Spondylolysis or Spondylolisthesis is permitted, as long as it is non-operative, the patient has not had any previous surgery for this, and no surgery is planned in the future
- 8) Completed standard-of-care procedures as outlined in Section 5
- 9) Subject consent and (if applicable) assent

3.4.2 Exclusion Criteria

- 1) Pregnancy (current)
- 2) Prior spinal or chest surgery
- 3) MRI abnormalities (could include syrinx >4mm, Chiari malformation, or tethered cord)
- 4) Neuromuscular, thoracogenic, cardiogenic scoliosis, or any other non-idiopathic scoliosis
- 5) Associated syndrome, including Marfan Disease or Neurofibromatosis
- 6) Sanders bone age greater than 4
- 7) Thoracic curve less than 35 degrees
- 8) Lumbar curve greater than or equal to 35 degrees

- 9) Unable or unwilling to firmly commit to returning for required follow-up visits
- 10) Investigator judgement that the subject/family may not be a candidate for the intervention

Subjects that do not meet all of the enrollment criteria may not be enrolled. Any violations of these criteria must be reported in accordance with IRB Policies and Procedures.

4 STUDY PROCEDURES

4.1 Screening Phase

4.1.1 Visit 1 (Screening & Pre-operative Visit) | Medical record and x-ray review | Hand x-ray to define bone age | Informed consent / assent | Physical Exam (research- including Adam's Forward bending test (degrees), thoracic and lumbar flexion (cm), thoracic and lumbar lateral flexion (cm) | Clinical photos | Pregnancy Test (Urine or Blood) as applicable | CBC blood test | SRS 30 Questionnaire | 4.2 Study Treatment Phase (Surgery) |

This phase includes the surgical intervention- Vertebral Body Tethering through anterior thoracoscopic approach under general anesthesia. This process is described in Section 2. Data from the surgery will be abstracted by medical record review for adverse events or complications. Intraoperative data (including radiographs) will also be abstracted from the medical record / surgical logs. Results from the surgery and inpatient stay will be abstracted at the time of discharge, except for those events which fall under the reporting guidelines of AE/SAEs. All AE/SAEs will be reported according to reporting guidelines listed in Section 8.

4.3 Post-surgical Follow-up Phase

This phase will include monitoring for post-operative complications / SAE, as well as two SOC clinical visits in this phase, where the subject will also undergo a research visit. Information from standard-of-care procedures will also be abstracted from the medical records and radiology databases.

4.3.1 Visit 3 (POD 45)
☐ Medical record review and abstraction
☐ X-ray review and abstraction
☐ Physical Exam (research)
☐ Complications Review
4.3.2 Visit 4 (POD 90)
4.3.2 Visit 4 (POD 90) ☐ Medical record review and abstraction
\square Medical record review and abstraction
 ☐ Medical record review and abstraction ☐ X-ray review and abstraction

4.4 Extended Follow-up Phase

This phase will include monitoring for post-operative complications/SAE, as well as three SOC clinical visits in this phase, where the subject will also undergo a research visit. Information from

standard-of-care procedures will also be abstracted from the medical records and radiology databases.

4.4.1 Visit 5 (POD 180)
☐ Medical record review and abstraction
☐ X-ray review and abstraction
☐ Physical Exam (research, including Adam's Forward bending test (degrees))
☐ SRS 30 Questionnaire
☐ Complications Review
_
4.4.2 Visit 6 (POD 365)
☐ Medical record review and abstraction
☐ X-ray review and abstraction
☐ Physical Exam (research- including Adam's Forward bending test (degrees), thoracic
and lumbar flexion (cm), thoracic and lumbar lateral flexion (cm)
☐ SRS 30 Questionnaire
□ Clinical Photos
☐ Hand x-ray to define bone age
□ Complications Review
4.4.3 Visit 7 (POD 730)
☐ Medical record review and abstraction
☐ X-ray review and abstraction
☐ Physical Exam (research- including Adam's Forward bending test (degrees), thoracic
and lumbar flexion (cm), thoracic and lumbar lateral flexion (cm)
☐ SRS 30 Questionnaire
☐ Hand x-ray to define bone age
□ Clinical Photos
☐ Complications Review
4.4.4 Visit 7 (POD 1095)
☐ Medical record review and abstraction
☐ X-ray review and abstraction
☐ Physical Exam (research- including Adam's Forward bending test (degrees), thoracic
and lumbar flexion (cm), thoracic and lumbar lateral flexion (cm)
☐ SRS 30 Questionnaire
☐ Hand x-ray to define bone age
□ Clinical Photos
☐ Complications Review
4.4.5 Visit 7 (POD 1460)
☐ Medical record review and abstraction
☐ X-ray review and abstraction
☐ Physical Exam (research- including Adam's Forward bending test (degrees), thoracic
and lumbar flexion (cm), thoracic and lumbar lateral flexion (cm)
☐ SRS 30 Questionnaire
☐ Hand x-ray to define bone age
□ Clinical Photos
☐ Complications Review
T

4.4.6 Visit 7 (POD 1825)

☐ Medical record review and abstraction
☐ X-ray review and abstraction
☐ Physical Exam Exam (research- including Adam's Forward bending test (degrees),thoracic
and lumbar flexion (cm), thoracic and lumbar lateral flexion (cm)
☐ SRS 30 Questionnaire
☐ Hand x-ray to define bone age
☐ Clinical Photos
☐ Complications Review

4.5 Unscheduled Visits

Unscheduled clinic visits will be made through the departments / hospitals clinical schedulers. As part of clinical care, physical evaluations and tests may be conducted. At these visits, the only research procedures performed will be medical record / radiographic record abstraction and complications review.

4.6 Subject Completion/Withdrawal

Subjects may withdraw from the study at any time without prejudice to their care. They may also be discontinued from the study at the discretion of the Investigator for lack of adherence to study treatment or visit schedules, AEs, or due to non-compliance. However, in order to collect important study-related data for this investigational device, as much as is feasible, the Investigator will make efforts to follow-up subjects who do not strictly adhere to timely visit schedules. The Investigator may do this via emails, phone calls, or letters. The Investigator may also withdraw subjects who violate the study plan, or to protect the subject for reasons of safety or for administrative reasons. It will be documented whether or not each subject completes the clinical study. If the Investigator becomes aware of any serious, related adverse events after the subject completes or withdraws from the study, they will be recorded in the source documents and on the CRF.

4.6.1 Early Termination Study Visit

Subjects that withdraw from the study prior to study completion will have all data collected to date kept on file. Subjects who wish to have their data removed from the study must submit a written request addressed to the site's PI. A 'Study Completion CRF' will be filed for each subject.

5 STUDY EVALUATIONS AND MEASUREMENTS

Patients will undergo standard of care for adolescent idiopathic scoliosis before research procedures are initiated.

New visit includes the following: ☐ Medical history ☐ Vitals ☐ Standing x-rays (pre-op Coronal / Sagittal / Bending Bolster Film) Cobb angle (measurement of spinal curve) ☐ Hand x-ray to determine skeletal maturity age Sanders score (0-7) to be used ☐ pre-pubertal skeletal maturity 7 skeletal maturity ☐ Clinical Photo
Follow-up Visit(s) ☐ Medical history ☐ Vitals ☐ Standing x-rays (pre-op Coronal / Sagittal Film) Cobb angle (measurement of spinal curve) ☐ Clinical Photo
Pre-op operative discussion for surgical indication 1. Pain 2. Thoraco-lumbar orthosis inadequately managing curve progression 5.1 Screening and Monitoring Evaluations and Measurements
5.1.1 Pre-operative Visit
5.1.1.1 Screening □ Potential subject identified by treating surgeon (match I/E criteria, surgical candidate) □ Informed Consent / Assent □ Review Inclusion / Exclusion Criteria, Complete I/E Checklist □ Subject Screening CRF
5.1.1.2 Pre-operative Medical Record / Radiograph Review Name Age Race Sex Ethnicity Date of Birth MRN Diagnosis Clinical and Surgical History (including history of pregnancy) Radiographic information and reports (including pre-op Coronal / Sagittal / Bending Bolster Films; Spine MRI) Clinical photos PFT Data (if available)

5.1.1.3 Pre-op Physical Examination
☐ Standing Height
□ Weight
☐ BMI – (reported as %) as calculated by the medical record
☐ Trunk flexibility measurements (standardized): Adam's Forward bending test / Inclinometer
(degrees), thoracic and lumbar flexion (cm), thoracic and lumbar lateral flexion (cm)
☐ Data abstracted from clinical care exam (medical records, radiology reports, pulmonology
tests)
☐ SRS 30 Questionnaire

5.1.2 Surgical Intervention and Post-operative Course 5.1.2.1 Intraoperative Data (abstracted from medical record)

 □ Operative time (Surgical Start time, Surgical End time) □ Intra-operative estimated blood loss □ Blood products utilized: cell saver (cc) given, other transfused blood products (cc) □ Number of portals □ Implant tracking Information: o Brand and model information of each implanted device o Part number, lot number, and UDI of device components: PET cord, set screws, vertebral screws, staples.
o Type and size of screws used o Length of PET cord used
 □ The extent of annulectomy (complete or partial) and the presence of pleural closure □ Whether a thoracoplasty was performed will be noted along with number of ribs and whether the pleura was cut or not (internal vs external thoracoplasty – if used) □ Posterior based Discectomy □ First Assistant information
☐ Antibiotic use
 □ Type and Dose of antifibrinolytic □ Time-Exposure of Flouroscopic X-ray during procedure □ Total intraoperative radiation dose
5.1.2.2 Post-surgical Data (abstracted from medical record)
 □ Chest tube drainage on day #1 - #5, and total collected □ Postoperative day of extubation as well as chest tube removal will be noted □ Postoperative day the patient was converted entirely to oral pain medication □ Visual Analogue Scores (measures the intensity of a child's pain experience) at discharge will be recorded. This is used to record the amount of back pain a patient is experiencing. □ Day of discharge will be recorded □ The use of a postoperative brace and the number of months utilized will be recorded □ Complications will be recorded: Post-operative complications will be recorded and status will be updated until resolved. This data collection methodology will be standardized via the complication form in the patient's study binder. □ Post-op Drain: type and drainage amounts daily until d/c of drain. □ Data abstracted from medical records, radiology reports, and surgical logs
5.1.3 POD-45 and POD-90 Follow-up
5.1.3.1 Post-Operative Visit
☐ Medical and radiographic record review
 □ Standing Height □ Weight □ BMI □ Trunk flexibility measurements (standardized): Adam's Forward bending test (degrees) only □ Data abstracted from clinical care exam (medical records, radiology reports, pulmonology tests)

5.1.4 POD-180, POD-365, POD-730, POD 1095, POD 1460, POD 1825 Follow-up

5.1.4.1 Extended Follow-up Visit

5.1.5 Laboratory Evaluations

5.1.5.1 Pregnancy Testing: Performed at Pre-op Visit only

A urine or blood pregnancy test will be performed for female subjects older than 11 years of age, or any female who has begun menses will be required to complete a urine or blood sample pregnancy test. Results of such testing will be provided to the study participant, unless it is determined that she is unable to understand the significance or implications of a positive test result. In this case, the parent (s) will be informed of the positive result. In the event of pregnancy, the participant will not receive the study intervention. Participants who are found to be pregnant will be advised to contact family planning counseling services.

5.1.6 Other Evaluations, Measures

	Sanders Bone Age: Attached as Supplement 1
	Adam's Forward Bending Test: Subject stands with their back to the examiner, and bends
	forward at the waist, with knees in extension. The examiner looks at the horizontal plane of the
	spine, and measures angle created between a rib hump and the horizontal plane. This is
	measured with an inclinometer.
	Thoracic/Lumbar Flexion test: Subject stands with trunk erect while measuring tape is placed
	proximally on the spinous process of C7 and distally to S1. The subject then bends forward at
	the waist, with knees in extension. Following flexion of the vertebrae, using the same bony
	landmarks, the examiner calculates the difference in distance between the starting and ending
	positions.
	Thoracic/Lumbar Lateral Flexion test: Subject stands erect with the feet flat on the floor. Place
	one end of a measuring tape on the tip of the middle finger and the other on the floor on a
	point directly beneath the middle finger. The patient then laterally flexes their trunk. The
	difference following the lateral flexion motion is measured.
	SRS 30: Attached as Supplement 2

5.2 Safety Evaluation

Subject safety will be monitored by recording all AEs and SAEs, and will be recorded on the complication form in the patient's study binder. The evaluation of safety is a primary objective of

this research study. There will be a clear classification of "device-related" adverse events. Device-related adverse events are those events directly related to the integrity, safety, or biomechanics of the device components: **PET cord, staples, set screws and vertebral screws.** This can include variables like device breakage or device migration. Other adverse events which are considered not device-related are those that are related to the act of surgery and medical recovery. The type of events will be documented on the CRF.

5.3 Efficacy Evaluation

The mode of efficacy evaluation for this procedure will be measurement of Cobb Angle. Cobb Angle is a coronal plane radiographic measurement of curvature of the spine. This angle will be recorded for the pre-operative coronal spine radiograph, as well as all subsequent serial radiographs. The change in Cobb angle (reduction) will be the primary evaluator of efficacy. 'Overall study success' of the intervention will be defined by a final Cobb angle of less than or equal to 50 degrees by the time subject reaches skeletal maturity.

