- 2) Post-operative active phase: Incidence of infection (within 90 days post-op), pneumothorax, bronpulmonary plug, or any reportable SAE.
- 3) Extended follow-up phase: Incidence of over-correction, implant failure (measured on serial x-ray), incidence of curve progression to >50 degrees at 5 year follow-up, or incidence of secondary surgery or re-operation to correct further spine deformity (not related to trauma or other issues not related to the initial surgery / disease).

Statistical And Analytic Plan

Cobb angle is a continuous variable. T-test or repeated measures Anova will be used to detect any change in Cobb angle post-operatively. Linear regression will be utilized to assess which variables are associated with change in post-operative Cobb angle.

DATA AND SAFETY MONITORING PLAN

The PI and Data Safety group will meet regularly to discuss any safety events. Group's reports will be forwarded to the IRB during continuing review per ORC monitoring guidance. Safety reporting will be according to IRB SOP 408 and governing FDA guidelines. The PI and study team will also comply with all ORC monitoring standards. The PI will meet with the study team regularly to discuss study progress and ensure data fidelity. The first meeting will take place before initiation of the study to discuss the protocol and establish guidelines to monitor the study. The Sponsor-PI will work in conjunction with the DSMB members to prepare an agenda to address the review of the initiation of the trial, reporting of adverse events, stopping rules, etc.

Meetings will be held before enrolling the 1st, 5th, 9th and so forth patient. If a Serious Adverse Event (SAE) occurs, a separate meeting will be held.

The meetings will be held at the Nemours AIDHC Department of Orthopedics using WebEx connectivity for attendees who are not in the office.

Meeting minutes will be recorded by the study coordinator and will become part of the study binder.

DSMB group includes the following members who do not have a financial or other types of conflict of interest related to this study:

- 1. [name] [name]
- 2. [name]
- 3. [name], [name]

[name] will not lead the DSMB meetings, but help to prepare reports/events for the DSMB. [name] will be present as a participant in the meetings to answer questions by the DSMB personnel, but will not be present for a closed portion of the meeting.

Members of the DSMB are:

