6.3.3 Efficacy Analysis

The primary analysis will be based on an intention to treat approach and will include all subjects who have undergone the intervention.

The endpoint used for efficacy will be change in post-operative Cobb angle compared to preoperative Cobb angle, measured on coronal radiograph of the spine. Considering change in Cobb angle is a continuous variable, repeated measures Anova or t-test will be used to detect any change in Cobb angle post-operatively. Linear regression will be utilized to assess which variables are associated with change in post-operative Cobb angle.

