6.6.2 Stopping rules for SAEs that are device-related
Definition of Terms:
□ Screw failure – screw and/or centering staple have loosened from the vertebra AND require re- operation
☐ Tether failure – the tether has broken or lost tension. Diagnosed at any time point after 3 months by increased angulation at a disc space on standing PA or increase in disc wedging on side bending x-ray to the side away from the implant. Also, it is only an SAE if noted before maturity AND overall Cobb worsens compared to the first erect measurement
☐ Implant re-operation - any problem with the implant that requires re-operation including re-operation for overcorrection with any of the following: a removal of all or part of the implant, loosening of the tension on the implant, or spinal fusion.

Stopping Points
☐ Screw failure stopping point: 3 of first 5 cases, 5 of first 10, or 25% of patients beyond 20
cases
☐ Tether failure stopping point: 3 of first 5 cases, 5 of first 10, or 25% of patients beyond 20
cases
☐ Implant failure re-operation stopping point: occurs in 4 of first 5 cases or greater than 50% of
cases beyond 10 cases

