8.4 Recording plan for AE / SAEs

Surgery and Post-operative Phase (Day 0 – POD 90):

For these phases, all AEs (including SAEs) will be noted in the study records and reported per IRB and FDA requirements outlined below. The subjects will be encouraged to contact the office with any concerns, and the medical record will be monitored by study staff for indications of AEs.

Extended Follow-up Phase (POD 91-POD 1825):

For this phase, all SAEs will be recorded (regardless of cause). Only AEs which are deemed "device related" will be recorded on study documents and reported per IRB and FDA requirements outlined below. The subjects will still be encouraged to contact the office with any concerns, and the medical record will be monitored by study staff for indications of SAEs or device-related AEs.

Only the AE/SAEs indicated above will be recorded in a patient-specific study binder, kept in the secure Orthopedics research office. The binder will contain a full description of the event, including the nature, date and time of onset, determination of non-serious versus serious, intensity (mild, moderate, severe), duration, causality, and outcome of the event. Hard copies of the primary documents (medical record notes) describing the event and any associated treatment will be printed and kept in the patient-specific study binder. A redundant copy of adverse events will be kept in the study REDCap database and will be maintained by the study team separately from the patient-specific study binder. The study binder will serve as the official record of all Events.

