9.3.2 Risk Assessment

This section outlines risks associated with the study procedures.

9.3.2.1 Surgical Procedure: Anterior-approach thoracoscopic vertebral body tethering (greater than minimal risk)

1. Investigational devise risks:

Implant failure (tether breakage, lost tension, screw pullout, screw fracture) overcorrection of curve, failure of correction, progression of curve and need for conversion to spinal fusion. Reoperation for any of the above listed reasons.

2. Anesthesia Risks:

Anesthesia effects alone or with the effects of surgery can be life threatening. Injury to the eyes, lips, teeth, nerves and/or spinal cord, increased or decreased blood pressure, irregular heartbeat, abnormal reaction to anesthesia agents. Some other known risk, side effects and potential complications include nausea and vomiting after surgery, excessive bleeding requiring blood transfusions. There are certain (very rare) risks of anesthesia including stroke, blindness, and long-term learning disability, which are unpredictable, not well understood and still being studied by doctors.

3. Surgery Risks:

Infection, bleeding, allergic reaction, significant scarring, need for additional surgery, and even death or disability. Some other known risks, side effects and potential complications include neurological deficit, visceral, or vessel injury, blindness, need for transfusion of

blood products, back pain, pulmonary insufficiency, pain and unforeseen medical complications. Risks associated with radiation exposure from fluoroscopy and X-rays.

4. Spine surgery risks:

Implant malposition, implant failure (rod breakage, screw pullout, screw fracture), progression of curve above or below corrected spinal region, pseudoarthrosis (non-union), need for additional surgery, vertebral body damage, paralysis, and allergic reaction to implants. Reoperation for any of the above listed reasons.

It should be noted that the above risks are the same risks that are present for standard-of-care surgery for spinal surgery. All appropriate clinical care procedures and pathways followed for standard-of-care spine surgeries will take place for these subjects.

9.3.2.2 Other Potential Risks (No greater than minimal risk study procedures):

- Review of medical records: There is a risk of breach of confidentiality and privacy as a result of medical record review. This risk is minimized as detailed in Section 9.

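### Overall success is defined by the final Cobb angle alone, so read literally a child fused after the tether fails, who ends at 50° or less, counts as a tether success

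*Combined protocol and SAP*

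**What the plan says.** **Success rule.** Section 5.3 states that overall study success "will be defined by a final Cobb angle of less than or equal to 50 degrees by the time subject reaches skeletal maturity". The angle is read from the pre-operative film "as well as all subsequent serial radiographs". No condition concerns later surgery.

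**Analysis set.** Section 6.3.3 describes its approach as intention to treat and says that the analysis "will include all subjects who have undergone the intervention". It does not say what to do with films taken after a re-operation or fusion.

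**Conversion is foreseen.** Section 9.3.2 lists among the risks of the device "overcorrection of curve, failure of correction, progression of curve and need for conversion to spinal fusion". Section 6.6.2 defines implant re-operation, for the stopping rules, as re-operation for an implant problem with "any of the following: a removal of all or part of the implant, loosening of the tension on the implant, or spinal fusion". The synopsis, under Safety Evaluations, names as extended-phase outcomes "incidence of curve progression to >50 degrees at 5 year follow-up, or incidence of secondary surgery or re-operation to correct further spine deformity". None of these places is linked to the success rule.

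**Withdrawal.** Section 4.6 lets the investigator withdraw a child "to protect the subject for reasons of safety or for administrative reasons", among other reasons, but does not name fusion as one. Section 4.6.1 keeps the data of withdrawn children collected up to that point.

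**The concern.** The study asks whether the tether controls the curve. A final angle of 50° or less can arise because the tether worked, or because it failed and a fusion then corrected the curve. The written rule does not separate the two.

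This matters because the protocol ties 50° to the need for fusion. Section 1.1.2.2 gives fusion as standard care at or near 50°, and Table 3 in Section 1.4.1 projects progression to surgery with that threshold. A child who passes 50° after tether failure reaches the protocol's own indication for fusion, and the fusion then lowers the angle on which success is judged. The rule can thus remove failures that it is meant to count.

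If the scoring is settled only at analysis, it will be chosen with the outcomes known, in an open-label, single-arm study.

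**Working it through.** The plan states no success rate, target or conversion rate, so there is no figure of its own to reproduce. The steps below show what the rule does.

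**1. Would a fused child be expected to meet the angle rule?**

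Inputs: threshold 50° (Section 5.3); upper entry limit 60° (Section 3.4.1), used as an example of the angle at fusion; mean correction after fusion 56–57% (cited studies in Section 1.3.1).

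- Correction needed to reach 50°: 1 − 50/60 = 16.7% from 60°; 1 − 50/55 = 9.1% from 55°.
- Angle after fusion from 60°: 60 × 0.44 = 26.4°; 60 × 0.43 = 25.8°.
- Pre-fusion angle above which the result would still exceed 50°: 50/0.44 = 113.6°; 50/0.43 = 116.3°.

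The 56–57% are means from fusion series, not from revision of failed tethers. They are used as an assumption. With them, most fused children would be expected to pass.

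**2. Effect on the success rate**

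Inputs: N = 30 (synopsis and Section 3.3.2, although 3.3.2 also says that there is no target enrolment). Assumptions: all 30 stay in follow-up and end at 50° or less, and k of them are converted to fusion. The values of k are chosen for illustration. Intervals are Clopper–Pearson.

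| k | As written | Conversion scored as failure: (30 − k)/30 |
|---|---|---|
| 0 | 30/30 = 100% (88.4–100) | 30/30 = 100% (88.4–100) |
| 1 | 30/30 = 100% (88.4–100) | 29/30 = 96.7% (82.8–99.9) |
| 3 | 30/30 = 100% (88.4–100) | 27/30 = 90.0% (73.5–97.9) |
| 6 | 30/30 = 100% (88.4–100) | 24/30 = 80.0% (61.4–92.3) |

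The difference is k/30, or 3.3 percentage points per conversion. The 100% follows from the assumption that all children end at 50° or less. What the table shows is that the written rate does not move with k.

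**3. Effect on mean Cobb change**

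The secondary endpoint (Sections 6.2 and 6.3.3) has the same gap. Assume fusion at 50–60° for progression or loss of correction, before the visit that is analysed. The fusion then credits the child with between 0° (at 50°, no correction needed) and 60 × 0.57 = 34.2°. The shift in a mean over 30 children is k × credited degrees / 30.

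- k = 1: 0 to 34.2/30 = 1.1°
- k = 3: 0 to 102.6/30 = 3.4°
- k = 6: 0 to 205.2/30 = 6.8°

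No direction is claimed for fusion after overcorrection, or for loosening or removal of the tether.

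**The case against.** The strongest reply is that this figure carries little weight and that conversion is already counted. Safety is the primary endpoint (Section 6.1). Overall success is not listed in Section 6.1 or 6.2 and has no analysis in 6.3.3. Re-operation for further deformity is an extended-phase safety outcome. Surgery under general anaesthesia for a complication is Grade IIIb in Appendix 1, hence an SAE, and SAEs of any cause are recorded to day 1825 (Recording plan for AE / SAEs). This stands. Conversions are not hidden, and most of a fusion-free rate could be derived later.

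A second reply is that an angle-only rule matches the stated aim in the abstract, which is to avoid progression past 50°. That is fair, and it is a reason to keep the angle-only rate as a companion figure. It does not justify crediting the tether with an angle that a fusion produced.

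A third is that Section 5.3 does not expressly say that the final film may be a post-fusion film. True, but it counts all serial films and makes no exception, so the literal reading includes them. Taking the last pre-fusion film instead would be a choice that the plan does not make. A child fused at or just below 50° would pass under either choice.

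Two stronger readings are tempting, and the documents do not support them:

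- A reader might infer that converted children who are withdrawn drop out of the denominator, so that the rate stays at 100%. Section 4.6.1 keeps their films, Section 6.3.3 includes all treated children, and a last film above 50° could be scored as a failure. Their scoring is undetermined.
- A reader might infer that the protocol adopts avoidance of fusion as its own criterion, because Section 1.1.2.1 reports bracing results that way. That section describes cited studies and sets no trial criterion.

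**Conclusion.** The concern holds in a limited form. Under the literal rule in Section 5.3, a child fused after tether failure or progression, who stays in follow-up and ends at 50° or less, is a success of the intervention, and nothing elsewhere in the document corrects this. With 30 children each such conversion is worth 3.3 percentage points. Six would separate a reported 100% from 80.0%, provided that all children end at 50° or less. The number of conversions is unknown, and the expectation that fused children pass rests on fusion series.

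No test, power statement or target depends on the rate, so no formal conclusion of the trial is invalidated. The harm is that the efficacy result may read better than the tether's own performance. It should be fixed before analysis, since the scoring rule is best set before the outcomes are known.

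**What to change.** **Section 5.3.** Define overall success as a Cobb angle of 50° or less at skeletal maturity and no conversion to spinal fusion. Score converted children as failures in the all-treated set, including any who were withdrawn. Give an exact 95% confidence interval and report the angle-only rate beside it. State how conversions after day 1825 but before maturity are ascertained from the medical record. SAE recording stops at day 1825 and participation at 1825 + 90 days (Section 3.3.1), so a child enrolled at 8 would be about 13 and may not yet be mature.

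**Section 6.3.3.** Keep the Cobb-change analysis of all observed films. Add one pre-specified analysis that does not use post-fusion films as tether outcomes, and report the number of children and films affected.

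**Cost.** A few sentences, one extra analysis, and a record check for children who mature after day 1825. Re-operations, SAEs and serial films up to day 1825 are already collected. The success rate may be less favourable. The change concerns scoring only and alters no treatment decision.
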